### **Adverse events & Serious adverse events:**

Adverse events and Serious adverse events (for definition, see Being a Parent-Enjoying Family Life study protocol v5. 279116) will be collected and reported as frequency and proportions from total sample.

## **1.4 Sample size estimation (including clinical significance)**

A total sample of n=72 is sufficient for precise feasibility parameter estimates: primary feasibility criterion is trial retention rate of at least 65%, based on median completion rates for PD diagnosis. A total sample of 72 allows 95% confidence that an anticipated 6-month follow up rate of 70% or larger will be estimated within  $\pm 10.7\%$  percentage point (Browne, 1995).

Process evaluation: A subgroup sample of 24 parents/caregiver participants for the process evaluation was decided based on both pragmatic reasons and to ensure saturation is reached. It is estimated that between 10-12 participants are needed to reach saturation in homogenous groups (Boddy, 2016). As we have two treatment groups, a sample of 24 should allow for sufficient saturation of themes regarding trial and intervention experience and acceptability. Purposive sampling will consider the effects of attendance on treatment experience, however as this is a feasibility study and there is no clear data on retention rates for the intervention, it is challenging to estimate the proportion of participants in each “attendance” group to sample from.

[figure not shown]
## **2. Data description**

### **2.1 Recruitment and representativeness of recruited patients**

CONSORT flow chart will be constructed (Eldridge et al., 2016; Moher et al., 2001) – see Figure 2. This will include the number of eligible patients, number of patients agreeing to enter the trial, number of patients refusing, then by treatment arm: the number of patients completing/non-completing treatment, the number continuing through the trial, the number withdrawing, the number lost to follow-up and the numbers excluded/analysed.

Completed treatment: defined by attending 5 or more sessions (not including coffee morning); Non-completion: defined as less than 5 completed sessions.

**Figure 2. Template CONSORT diagram for BAP-EFL trial**

## **2.2 Baseline comparability of randomised groups**

Baseline descriptions (demographics and all outcome measures) of participants by treatment arm and overall will be reported as: means and standard error or numbers and proportions as appropriate. No significance testing will be conducted.

## **2.3 Adherence to allocated treatment and treatment fidelity**

Compliance with treatment will be described in terms of number of group sessions attended in each trial arm. The reasons for withdrawal from treatment or non-attendance where available will be summarised. The mean number of sessions attended will be compared across arms. The baseline demographic characteristics of those in each attendance group (Low attenders (<5 sessions), high attenders (5 or more) and non-attenders) will be compared in each trial arm and any statistically significant patterns reported.

Treatment fidelity will be summarised by trial arm. Checklists measuring fidelity developed for both arms will be completed by Parent Group facilitators together after each session. Fidelity to session content and delivery is scored from 0-2 (0=no, 1= not sure, 2= yes) across four items (content, time management, facilitation methods, delivery). Fidelity will be reported as a total score (out of 80 for EFL groups and 72 for BAP) and percentage for each group in each arm. Any missed content identified in the fidelity measure will be reported.

## **2.4 Loss to follow-up and other missing data**

The proportions of participants missing each variable will be summarised in each arm and at each time point. The baseline demographic characteristics of those missing follow up will be compared to those with complete follow up and any statistically significant patterns reported. The reasons for withdrawal from the trial will be summarised.

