# **3. Data analysis plan**

## **3.1. Feasibility outcomes, adherence outcomes and progression criteria**

Feasibility and adherence outcomes will be summarising using descriptive statistics: number, percentages and proportions, mean and standard deviation as appropriate. These outcomes will be presented overall and also separately by arm in the

CONSORT diagram. The outcomes will be evaluated against pre-specified feasibility parameters as above (page 5) . No inferential statistics will be carried out on these feasibility outcomes.

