#### *Missing outcome data*

No inferential statistics will be conducted. Correlational analysis will assess whether attendance correlates with missing outcome data. T-tests will be used to compare number of missing outcomes in intervention and control arms. If there is missing outcome data, we will investigate to see if any baseline variables are predictors of outcome missingness. Such variables could then be included as covariates in the model if deemed suitable for adjustment.

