#### *Method for handling multiple comparisons*

This study is underpowered to report significance test, therefore no correction for multiple comparison need be applied.

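### Demographic patterns of attendance and dropout are selected for reporting by underpowered, unadjusted tests, and missingness is t-tested, against the SAP's own no-inference rule

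*SAP*

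**What the plan says.** Three places in the SAP call for significance testing on who stayed and who attended.

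- Section 2.4, on loss to follow-up: "The baseline demographic characteristics of those missing follow up will be compared to those with complete follow up and any statistically significant patterns reported".
- Section 2.3, on the demographics of non-attenders, low attenders and high attenders: these "will be compared in each trial arm and any statistically significant patterns reported".
- Section 3.1.2, Missing outcome data: "T-tests will be used to compare number of missing outcomes in intervention and control arms". The opening sentence of the same paragraph says that no inferential statistics will be done. The paragraph also plans a correlation of attendance with missingness and a search for baseline predictors of missingness, which may become model covariates if judged suitable.

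Other places point the opposite way.

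- Section 3.1, on feasibility and adherence outcomes: "No inferential statistics will be carried out on these feasibility outcomes". Section 1.3 lists response, retention and session attendance among the feasibility outcomes.
- Section 3.1.2, on multiple comparisons: "This study is underpowered to report significance test, therefore no correction for multiple comparison need be applied".
- Section 2.2 excludes significance testing when baseline variables are compared between arms.

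No alpha, test or variable list is given for the comparisons in 2.3 and 2.4. Section 2.4 does not say which follow-up is meant, or whether the comparison is overall or by arm.

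Some reporting carries no significance condition. Section 2.4 states: "The proportions of participants missing each variable will be summarised in each arm and at each time point". Reasons for withdrawal, response rates in both arms and sessions attended by arm are likewise reported unconditionally (sections 1.3, 2.3, 2.4).

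**The concern.** There are two defects.

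The first is a contradiction. A t-test is inferential, so the missing-outcome paragraph cannot be followed as written. The tests in 2.3 and 2.4 concern retention and attendance, which section 3.1 says will not be tested. The SAP uses low power to waive multiplicity correction, yet relies on significance to decide which patterns to report.

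The second is that significance is a poor selection rule at this sample size. Retention at Time 2 is a primary progression parameter, and objective 3 is to investigate how participant and service factors influence trial methods, acceptability and fidelity. The profile of those lost, or of those who did not attend, is therefore information the definitive trial needs. Under the filter, a moderate real difference can go unreported because 22 or so dropouts cannot make it significant, while a chance difference among several characteristics is put forward as a pattern.

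**Working it through.** **Inputs.** From section 1.4: N = 72 ("A total sample of n=72 is sufficient for precise feasibility parameter estimates") and a 70% follow-up rate ("6-month follow up rate of 70% or larger will be estimated within" ±10.7 points). Then 0.70 × 72 = 50.4, so about 50 are retained and 22 missing. Assumed, because the SAP does not state them: two-sided alpha of 0.05, and 1:1 allocation (36 per arm).

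The number of characteristics is taken as 8 to 12 from the baseline list in section 1.3. Eight counts age, sex and ethnicity for parent and child (6), household composition (1) and socioeconomic status as one item (1). Twelve splits socioeconomic status into income and each parent's education (3) and adds current mental health treatment and previous parenting intervention (2): 6 + 1 + 3 + 2 = 12.

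**The plan's own figure.** 1.96 × √(0.7 × 0.3 / 72) = 10.6 points. With 71 in the denominator it is 10.66, which rounds to the stated 10.7. The figure reproduces.

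**Power of the filter for a binary characteristic, 50 retained v 22 missing.** Exact enumeration: power = Σ over x, y of Bin(x; 50, p1) × Bin(y; 22, p2) × [test rejects at 0.05].

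| Retained v missing | Fisher's exact test | t-test on 0/1 |
|---|---|---|
| 50% v 70% | 31% | 35% |
| 30% v 50% | 32% | 40% |
| 25% v 50% | 48% | 57% |
| 50% v 80% | 64% | 69% |

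**Power for a continuous characteristic.** Noncentral t on 70 df, critical value 1.994, noncentrality d × √(50 × 22 / 72) = 3.909d.

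- d = 0.3: noncentrality 1.17, power 21%.
- d = 0.5: noncentrality 1.95, power 49%.
- d = 0.8: noncentrality 3.13, power 87%.

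For attendance within one arm, an assumed 24 v 12 split gives 28% for d = 0.5 and 59% for d = 0.8.

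**False patterns.** For k independent tests at 0.05, the chance of at least one false positive is 1 − 0.95^k.

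- k = 8: 1 − 0.663 = 34%.
- k = 12: 1 − 0.540 = 46%.

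Counting one attrition set and one attendance set in each arm, 12 × 3 = 36 tests give 84%. Correlated characteristics lower all of these figures.

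**What an estimate would show instead.** Between-arm difference in missingness, 20% v 40% with 36 per arm: 1.96 × √(0.2 × 0.8 / 36 + 0.4 × 0.6 / 36) = 1.96 × 0.105 = ±21 points. Binary characteristic, 50% of 50 v 70% of 22: 1.96 × √(0.25 / 50 + 0.21 / 22) = ±24 points. Standardised difference of 0.5: 1.96 × √(72 / 1100 + 0.25 / 144) = ±0.51. These are wide, but the uncertainty is visible.

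**The case against.** A reader might infer that real differential dropout between arms will be concealed. The SAP does not support that. Missing proportions by arm and time point, reasons for withdrawal, response rates and attendance by arm are reported whatever any test shows, and nothing makes that reporting depend on the t-test. The low power of the t-test (46% for 20% v 40%, treating missingness as yes/no) therefore hides no rate.

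Other points on this side also stand:

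- Sections 2.3 and 2.4 say that significant patterns are reported. They do not say that only these are, although that is the natural reading.
- Very large differences would usually pass the filter (87% power at d = 0.8).
- A false pattern is not certain. Income, education and household composition are likely to be correlated, and the total number of tests is not fixed by the SAP. Higher totals, such as 48 tests with T2 and T3 tested separately, rest on assumption.
- The no-test wording in 3.2 and 3.2.1 concerns treatment effects. The conflict is explicit within the missing-outcome paragraph. For 2.3 and 2.4 it depends on how far section 3.1 and the multiple-comparisons paragraph reach.
- The covariate sentence sets no significance rule, and adjusting for predictors of missingness is a recognised approach.
- Barriers to attendance and to data collection are also explored in the qualitative interviews (section 5.1).

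These points narrow the concern to the demographic comparisons and the t-test. They do not remove the contradiction or make the filter a sound rule.

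**Conclusion.** Wrong as written, and worth correcting. The missing-outcome paragraph contradicts itself. The significance filters in 2.3 and 2.4 run against the rule for feasibility outcomes in 3.1 and the SAP's own statement on power. The consequence is limited to the description of who was lost or did not attend: moderate differences would be missed about half the time or more, and each set of comparisons carries roughly a one-in-three to nearly one-in-two chance of a false pattern if the tests are independent. The sizes rest on the assumed alpha, allocation and count of characteristics, and on the SAP's anticipated 70% follow-up. No progression criterion and no by-arm dropout rate depends on these tests, so a reader should not conclude that either is compromised.

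**What to change.** - In 2.3 and 2.4, delete the clause that ties reporting to statistical significance. Tabulate every listed baseline characteristic by follow-up status, overall and by arm, naming T2 and T3, and by attendance group within arm. Give differences or standardised differences and no p-values.
- In the missing-outcome paragraph of 3.1.2, replace the t-test with the between-arm difference in proportion missing at T2 and at T3, each with a 95% CI. The proportions by arm are already planned, so only the difference and its interval are new.
- The correlation of attendance with missingness may stay, labelled as a descriptive estimate.

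The cost is SAP wording and a slightly larger descriptive table. No additional data are needed.

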## **2.5 Adverse event reporting**

Serious adverse events (SAE) and Serious adverse reactions (SAR) will be summarised by arm. Individual adverse events (AE), adverse reactions (AR) will also be summarised and reported.

## **2.6 Assessment of outcome measures (unblinding)**

This is a single blind study, with the researcher only blind to intervention arm. Evidence for unblinding of treatment to researchers will be recorded and reported.

## **2.7 Descriptive statistics for outcome measures**

Each outcome measure will be described by treatment group. A description of the T1, T2 and T3 outcomes total and subscales scores will be presented in a table using means and standard error for continuous data, or medians and interquartile ranges if data are skewed. Frequencies and proportions will be reported for categorical variables.

## **2.8 Description of therapists/therapies**

The number of sessions offered per group and training for parent group leaders in each arm will be outlined in text or table format in line with TiDIER framework (Hoffmann et al., 2014).

# **3. Data analysis plan**

## **3.1. Feasibility outcomes, adherence outcomes and progression criteria**

Feasibility and adherence outcomes will be summarising using descriptive statistics: number, percentages and proportions, mean and standard deviation as appropriate. These outcomes will be presented overall and also separately by arm in the

CONSORT diagram. The outcomes will be evaluated against pre-specified feasibility parameters as above (page 5) . No inferential statistics will be carried out on these feasibility outcomes.

### **3.2 Preliminary estimation of treatment differences**

The aim of analysis of treatment differences is to give an indication of the potential range of effect sizes from BaP-EFL compared to standard BaP. Analyses will estimate the difference in mean outcomes between patients randomised to BAP-EFL and EPEC-BAP following an intention-to-treat principle (i.e. all data from randomised participant will be included in analysis, regardless of attendance). Group difference estimates (i.e. change from baseline) and associated 95% confidence intervals will be reported comparing BaP-EFL and EPEC-BaP across T2 and T3. Cohen's d will indicate size of effect. Inferential statistics and p-values will not be reported and estimates obtained will not be used to claim strong evidence for the effectiveness or ineffectiveness of the intervention as the trial is not powered to detect differences between arms.

#### **3.2.1 Analysis of primary and secondary outcomes**

No inferential statistics will be conducted on primary or secondary clinical outcomes, instead descriptive statistics will estimate the likely range of treatment effects (by reporting means and standard deviation) at post-treatment and 6-month follow up. Cohen's d and 95% CIs will be reported. For the primary clinical outcome of child behaviour, proportions of children scoring above the clinical cut off of  $\geq 131$  for the Intensity Scale and  $\geq 15$  for the problem scale will be reported at each time point. Mean difference in change from baseline, and 95% confidence intervals will be reported for all outcomes and subscales, but no comparison of treatment effect will be carried out.

Population variances for future power calculation will be determined using the upper 80th percentile of confidence intervals around the estimated population variance, as recommended by Browne (1995).

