##### *Stratification and clustering*

Randomisation was stratified by covariates: online or in person preference and currently receiving mental health treatment. These will be included as co-variates in the analysis. As the intervention occurs in groups, a group effect is possible and the model will include group as a co-variate to account for clustering within group.

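### Arm differences are estimated as change from baseline without adjusting for the baseline score, which costs precision; separately, SAP 3.2.1 rules out the comparison that it and 3.2 promise

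*SAP*

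**What the plan says.** Section 3.2 sets the aim of the treatment-difference analysis, which is to "give an indication of the potential range of effect sizes from BaP-EFL compared to standard BaP". It says the analyses estimate the difference in mean outcomes between arms, and then gives the scale: "Group difference estimates (i.e. change from baseline) and associated 95% confidence intervals will be reported", for BaP-EFL against EPEC-BaP at T2 and T3. Cohen's d is to express the size of effect, and p-values are excluded.

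Section 3.2.1 repeats the scale: "Mean difference in change from baseline, and 95% confidence intervals will be reported for all outcomes and subscales". The same sentence ends: "but no comparison of treatment effect will be carried out". That section also promises Cohen's d with 95% CIs. Neither section names the SD that divides the difference to give d.

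Under Stratification and clustering (3.1.2), the SAP names online or in-person preference and current mental health treatment as the stratification factors and says: "These will be included as co-variates in the analysis". Group is added to the model for clustering. The baseline outcome score is not listed. Missing outcome data allows further baseline variables only if they predict missingness and are judged suitable. Missing baseline data says that participants who did not complete baseline assessments were not randomised.

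**The concern.** There are two separate defects.

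The first is the estimator. Subtracting the baseline score treats the slope of follow-up on baseline as 1. When the correlation is below 1 and the SDs are similar, the true slope is smaller, so subtraction over-corrects. This adds noise and carries part of any chance baseline difference into the estimate. The baseline outcome is not a stratification factor, so allocation does not directly limit such a difference. The section exists to give a range of effect sizes, so a range wider than the data require defeats part of its purpose.

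The second is clarity. A between-arm difference with a confidence interval and a standardised effect is a comparison of treatment effect. A plan that promises these and also says there will be no comparison can be cited for either course. The missing denominator for d adds to this, because d is the named summary of effect size and its value depends on that choice.

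**Working it through.** **The plan's own precision figure.** The only one concerns follow-up, not treatment differences. Section 1.4 says: "A total sample of 72 allows 95% confidence that an anticipated 6-month follow up rate of 70% or larger will be estimated within" 10.7 percentage points either way. With p = 0.70 and n = 72, 1.96 × √(0.70 × 0.30 / 72) gives 10.59 points; with n − 1 in the denominator it gives 10.66, which rounds to 10.7. The figure reproduces. The SAP gives no precision for the arm difference.

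**Inputs for the estimator.** n = 72 and 70% follow-up come from 1.4; 0.70 × 72 = 50.4, so 50 analysed. Equal arms (25 each) are assumed. The correlation rho between baseline and follow-up is not in the SAP and is taken over 0.3 to 0.9. SDs are assumed equal at baseline and follow-up. Clustering and the other covariates are ignored.

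**Large-sample ratio.** The variance of the arm difference is proportional to 2σ²(1 − rho) for change and to σ²(1 − rho²) with baseline adjustment. The ratio of adjusted to change is (1 − rho²) / [2(1 − rho)] = (1 + rho)/2, and the CI narrows by 1 − √[(1 + rho)/2].

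**Half-widths with 50 analysed, in outcome SD units.** Change: t(48) × √(2/25) × √[2(1 − rho)]. Adjusted: t(47) × √(2/25) × √(1 − rho²) × √(1 + 1/46), where the last factor is a small-sample correction.

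| rho | (1+rho)/2 | CI narrower, large sample | Change, n = 50 | Adjusted, n = 50 |
|---|---|---|---|---|
| 0.3 | 0.65 | 19% | 0.673 | 0.549 |
| 0.5 | 0.75 | 13% | 0.569 | 0.498 |
| 0.7 | 0.85 | 8% | 0.441 | 0.411 |
| 0.9 | 0.95 | 3% | 0.254 | 0.251 |

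With 50 analysed, the narrowing is 18%, 12%, 7% and 1% (for example 1 − 0.549/0.673 = 18%). With all 72 analysed, the half-widths for change and adjusted are 0.556 and 0.452, 0.470 and 0.410, 0.364 and 0.338, and 0.210 and 0.206.

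The unadjusted comparison of follow-up means has a half-width of 0.569 with 50 analysed. At rho = 0.3 the change score (0.673) is therefore less precise than ignoring baseline altogether; the two are equal at rho = 0.5.

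**Chance imbalance.** Given an observed baseline difference D, the change-score estimate is displaced on average by −(1 − rho)D: 70%, 50%, 30% and 10% of D at the four values of rho.

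**Denominator of d.** SD of change divided by outcome SD is √[2(1 − rho)], which is 1.18, 1.00 and 0.77 at rho 0.3, 0.5 and 0.7. Dividing by the SD of change instead of the outcome SD multiplies d by 1/1.18 = 0.85 at rho 0.3, by 1.00 at 0.5 and by 1/0.77 = 1.29 at 0.7 (ratio 0.775 before rounding). That is −15% to +29%.

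**The contradiction.** No arithmetic applies. Section 3.2 reports group differences with intervals and d comparing the two arms. Section 3.2.1 reports mean difference in change with intervals and d, and then excludes any comparison. The second statement cannot be met if the first is carried out.

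**The case against.** The strongest reply is that little depends on this. Progression is decided on retention, SAPAS rate, recruitment, acceptability and fidelity, none of which uses the arm difference. Section 3.2 disclaims any conclusion on effectiveness. The gain also rests on an unstated rho and nearly vanishes when rho is high. All of this stands and limits the weight of the point. It does not remove it, because the SAP chose to report between-arm estimates, intervals and d, and the improvement needs no extra data.

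On the contradiction, 3.2 excludes p-values, 3.2.1 opens by excluding inferential statistics, and the multiplicity paragraph calls the study underpowered for significance tests. The disputed clause most plausibly means that no hypothesis test will be done. That is accepted, but the SAP does not say so.

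Four stronger readings are tempting and are not supported:

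- That the change score is a wrong or biased estimator. Randomisation makes it unbiased; the loss is in efficiency and in exposure to chance imbalance.
- That the arm difference is a raw one. Stratification and clustering puts two factors and group in the model. Section 3.2 also speaks of a difference in mean outcomes before equating it with change, so the scale itself is not stated cleanly.
- That the variance passed to the definitive trial would be that of the change score. Section 3.2.1 speaks of population variances, and objective 4 in 1.1 of variance estimates for parent and child outcomes. Neither says change.
- That the disagreement within 3.2 and 3.2.1 reduces precision. It makes the planned analysis unclear but widens no interval.

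**Conclusion.** The point holds as one of efficiency and clarity. The SAP reports arm differences as change from baseline and lists covariates that omit the baseline outcome score, although that score is required before randomisation. Adjustment would narrow the 95% CI by about 19% at rho 0.3, falling to about 3% at rho 0.9, and slightly less after small-sample correction with 50 analysed. These figures assume equal SDs and equal arms and leave out clustering and the other covariates; rho is an assumption throughout. Separately, the no-comparison clause in 3.2.1 contradicts the between-arm results promised in 3.2 and 3.2.1, and d is undefined to the extent of about −15% to +29% for rho 0.3 to 0.7. The progression decision is unaffected.

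**What to change.** - Under Stratification and clustering, add the baseline score of the same measure to the covariates. In 3.2 and 3.2.1, report the adjusted mean difference with 95% CI and no p-value at T2 and T3. If change is kept as the response, adding the baseline covariate gives the same treatment estimate.
- In 3.2.1, reword the end of the sentence to say that no hypothesis test of treatment effect will be carried out.
- State the SD that divides the difference to give d. The pooled baseline SD is one option; what matters is that one is named in advance.
- Report the baseline to follow-up correlation for each outcome, so that the definitive trial can be sized for a baseline-adjusted analysis.

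The handling of group is left as the SAP has it. The cost is SAP wording and one further model parameter per outcome. No new data are needed, because baseline and follow-up scores are already part of the plan.
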